Due to poor recruitment levels with our original study design, we are requesting a revision of the protocol to reflect updated study procedures. As of 9/28/17- we have enrolled one patient in the study who has completed all study procedures. The data for this 1 participant will be analyzed, but not included in the total n for STUDY 2. This participant has completed all study procedures and will not be informed directly that the study 1 has been modified to STUDY 2, as the modification was not due to concern of risk to subjects, rather that a sufficient number of subjects in our local community did not meet eligibility criteria..

Our revised protocol (named STUDY 2), instead of focusing on both naturalistic dual use behaviors and behaviors while switching to e-cigarettes, now is focusing only on the naturalistic behaviors of 32non-treatment seeking young adult e-cigarette/combustible tobacco product dual users. Combustible tobacco products include **cigarettes, cigars, cigarillos, hookah, roll your own cigarettes**).

In this one-year pilot study of 32 non-treatment seeking young adult e-cigarette/combustible tobacco product dual users (16 males/16 females), we will use smartphone-based ecological momentary assessment (EMA) to gather real-time data of e-cigarette and combustible tobacco product behaviors during a naturalistic 1-week combustible tobacco product/e-cigarette dual use period. (1) Participants will respond to daily random prompts assessing in-the-moment use of e-cigarettes/cigarettes and the subjective factors (ratings of satisfaction and withdrawal) and contextual factors (location, activity, social cues) associated with each episode of use. They will also complete daily electronic diaries to document e-cigarette use episodes/day, amount of e-liquid used, cigarettes smoked/day, nicotine concentrations and flavors used during the day, and how satisfied they were with the e-cigarette experience during the study. They will be queried about whether they changed product constituents (flavors, numbers of flavors, nicotine concentrations). We will also collect markers of carbon monoxide and nicotine exposure (CO, cotinine) throughout the study.

STUDY 2

Aim 1: To determine how within-subject's ratings of subjective factors (withdrawal, satisfaction with tobacco products) change between episodes of e-cigarette use vs. episodes of other combustible tobacco product use (cigarettes, cigars, cigarillos and/or hookah).

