Hypothesis A: Young adult dual users, particularly males, will report lower satisfaction and higher withdrawal scores with episodes of e-cigarette use, in comparison to episodes of combustible tobacco product.

Aim 2: To examine gender differences in e-cigarette use patterns among young adult dual users.

Aim 3: To examine gender differences in e-cigarette use patterns among young adult dual users.

Hypothesis B: Young men will be more likely smoke/vape for the rewarding effects of nicotine.

Hypothesis C: Young women will be more likely to smoke/vape in response to contextual reasons.

Exploratory Aim: To examine sex differences in within-subjects' changes in cotinine levels during the dual use periods.

STUDY 2

2. Research Plan:

- a. **Overview:** In this one-year pilot study of 32 non-treatment seeking young adult e-cig/combustible tobacco product dual users (15 males/15 females), we will use smartphone-based ecological momentary assessment (EMA) to gather real-time data of e-cigarette and combustible tobacco product behaviors during a 1-week cig/e-cigarette dual use period. Participants will be eligible if they self-report use of e-cigarettes at least one day during the past 7 days and use of at least one other combustible tobacco product at least one day during the past 7 days. Participants will respond to daily random prompts assessing in-the-moment use of e-cigs/combustible tobacco products and the **subjective factors** (ratings of satisfaction and withdrawal) and **contextual factors** (location, activity, social cues) associated with each episode of use. They will also complete daily electronic diaries to document e-cigarette use episodes/day, amount of e-liquid used, combustible tobacco products smoked/day, nicotine concentrations and flavors used during the day, and how satisfied they were with the e-cigarette experience during the study. They will also be queried about whether they changed product constituents (flavors, numbers of flavors, nicotine concentrations). We will also collect markers of carbon monoxide and nicotine exposure (CO, cotinine) throughout the study.

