- b. **Settings:** We will recruit participants from Southeastern CT (New Haven County, CT; 75% White, 13% Black, 3% Asian; ethnicity: 15% Latino). We expect some participants will be college students from other areas, thus generalizing our findings. Baseline study visits will occur at the APT Foundation, Inc. and follow-up visits may occur at APT, CSRU or public locations (i.e. coffee shops, libraries etc.)
- c. **Participants:** See Inclusion and Exclusion Criteria
- d. **Procedures:**

Recruitment and Screening: Our team has developed an age-appropriate, targeted strategy for recruitment (see III). Potential participants will be recruited through flyers, targeted advertisements on Facebook, Craigslist, and on public boards in local colleges, and through the Yale Center for Clinical Investigation volunteer database. Screening options will be provided (phone/text, or the Yale Qualtrics online survey system). We are confident we can recruit 3-4 participants/month over 9 months to reach sample size of n=30 32 in 1 year.

Study Entry: We will contact participants who meet inclusion criteria to schedule an in-person assessment at APT Foundation, Inc. Potential participants will meet with the Study Research Associate to be re-screened for eligibility. Women will provide a urine sample to verify pregnancy status. We will collect breath CO and salivary cotinine samples. After obtaining written consent, participants will complete a battery of baseline questionnaires. The RA will ask participants to provide cell, home, and work phone numbers, addresses, and contact information for at least 2 locators. The RA will notify each participant of the time of their next assessment by text/phone and mail. If after 3 attempts by telephone/text the participant cannot be contacted, the RA will contact the other 2 locators. We will also use this method to contact participants if they have ≥ 24 hours of missing data.

STUDY 2

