h. **In-person study visits:** In-person visits will occur in public places or study offices at baseline and follow-up. In addition to the CM procedures for CO monitor video submission, saliva cotinine samples will be collected at baseline, and follow-up to explore changes in cotinine levels.

3. Genetic Testing N/A

4. **Subject Population:** Provide a detailed description of the types of human subjects who will be recruited into this study.

STUDY 2

We plan to recruit 32 non-treatment seeking young adult e-cig/cigarette dual users (15 males/15 females), who use both e-cigarettes and combustible tobacco products. See V.7 for Inclusion/Exclusion Criteria.

5. **Subject classification:** Check off all classifications of subjects that will be specifically recruited for enrollment in the research project. Will subjects who may require additional safeguards or other considerations be enrolled in the study? If so, identify the population of subjects requiring special safeguards and provide a justification for their involvement.

 Children	 Healthy	 Fetal material, placenta, or dead fetus
 Non-English Speaking	 Prisoners	 Economically disadvantaged persons
 Decision ally Impaired	 Employees	 Pregnant women and/or fetuses
 Yale Students	 Females of childbearing potential	

NOTE: Is this research proposal designed to enroll children who are wards of the state as potential subjects? Yes No (If yes, see Instructions section VII #4 for further requirements)

6. **Inclusion/Exclusion Criteria:** What are the criteria used to determine subject inclusion or exclusion?

STUDY 2

Inclusion Criteria. Each participant must:

- (1) be 18 through 29 years of age;
- (2) **use at least one type of combustible tobacco product (cigarettes, cigars, cigarillos, hookah, roll your own cigarettes) on at least 1 day during the past 7 days (DURING the PAST 7 days, on how many days did you use a combustible tobacco product ? (1 or more)**
- (3) **use e-cigarettes on at least one day during the past 7 days**
- 4) have access to an e-cigarette
- (5) fluent in English;
- (6) have a functioning cell phone for personal use with wireless, camera, and application (via Apple or Android platform) capability;

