a. Justification of Sample Size: Estimation of sample size (n=32) is based on achieving a clinically meaningful precision in effect size estimates for the primary outcome of interest. With 30 subjects we will be able to construct a 95% CI for the mean change in e-cigarette episodes/day from week 1 to 2 of width up to 0.37 standard deviations away from the mean (Aim 1) and 95% CI for the slopes of the regression relationships in Aim 2 of half-widths up to approximately 0.67 of the corresponding slope values. The obtained interval estimates will be used to inform future larger definitive studies.

Analysis Plan: Aim 1 will determine how within-subject's ratings of subjective factors (withdrawal, satisfaction with tobacco products) change between episodes of e-cigarette use vs. episodes of other combustible tobacco product use (cigarettes, cigars, cigarillos and/or hookah)

During e-cigarette and combustible tobacco product use periods. We will evaluate the variability in levels of satisfaction and withdrawal scores during these periods. Correlations between repeated measures on an individual will be modeled with random subject effects. Aim 2 will evaluate gender differences in e-cigarette use patterns among young adult dual users mean changes in e-cigarette use between the dual use and exclusive e-cigarette use period that differ by sex. We will evaluate changes in contextual factors and will assess effect sizes and construct 95% CIs for change in e-cigarette use

12. Data Management:

Quantitative outcomes will be collected using paper forms which will be double entered into a secure database. Error checking and data validation will occur weekly and any problems will be queried and resolved immediately. [name] will create monthly data quality reports to check for completeness and accuracy of key variables, as well as rates of recruitment, retention, and follow-up. Baseline demographics and smoking behaviors will be summarized. Continuous data will be expressed as mean values with standard deviations and categorical data will be presented as counts with percentages.

SECTION VII: RECRUITMENT/CONSENT AND ASSENT PROCEDURES

1. Targeted Enrollment: Give the number of subjects:

- a. targeted for enrollment at Yale for this protocol_32
- b. If this is a multi-site study, give the total number of subjects targeted across all sites _____

2. Indicate recruitment methods below. Attach copies of any recruitment materials that will be used.

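### The planned 32 participants are split 15/15 by sex in two sections and 16/16 in a third, and the precision calculation uses 30, with nothing to reconcile them

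*Combined protocol and SAP*

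**What the plan says.** The combined protocol and SAP gives the Study 2 sample size in several places, all in current text.

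- Study 2 summary, before the aims: "In this one-year pilot study of 32 non-treatment seeking young adult e-cigarette/combustible tobacco product dual users (16 males/16 females").
- Section 2, Research Plan, a. Overview: "In this one-year pilot study of 32 non-treatment seeking young adult e-cig/combustible tobacco product dual users (15 males/15 females").
- Section 4, Subject Population: "We plan to recruit 32 non-treatment seeking young adult e-cig/cigarette dual users (15 males/15 females").
- Section 11a, Justification of Sample Size, opening: "Estimation of sample size (n=32) is based on achieving a clinically meaningful precision".
- Section 11a, next sentence: "With 30 subjects we will be able to construct a 95% CI for the mean change in e-cigarette episodes/day from week 1 to 2". The half-width given there is at most 0.37 SD, labelled Aim 1. A second figure, labelled Aim 2, is a half-width of about 0.67 of the slope.
- Section VII, item 1, Targeted Enrollment: 32.

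The one participant who completed the original design is analysed but expressly kept out of the Study 2 total.

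**The concern.** Two sections state a total that their own sex split does not produce. A third section gives a different split. The paragraph that justifies the total then calculates with another number. A reader cannot tell whether 30 is a leftover, an expected evaluable number or the intended sample.

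The split matters more here than in most pilots. Aim 2 concerns gender differences, and Aim 3 repeats it word for word. Hypotheses B and C contrast young men with young women, Hypothesis A singles out males, and the exploratory aim is about sex differences in cotinine. The number per sex is therefore the sample size for those comparisons. The study's declared product is a set of interval estimates for planning larger studies, so the precision statement should belong to the stated sample and to quantities that the study measures.

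**Working it through.** **Head counts.** 15 + 15 = 30, beside a stated 32 (Overview, Subject Population). 16 + 16 = 32, beside a stated 32 (Study 2 summary). The gap of 2 is not explained by the single participant from the original design. No dropout, non-compliance or evaluability allowance appears in the sample-size paragraph or elsewhere.

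**Reproducing the plan's Aim 1 figure.** For one mean (or one mean change), the 95% half-width in SD units is t(0.975, n−1)/√n.

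- n = 30: 2.045/5.477 = 0.3734, which rounds to the stated 0.37.
- n = 31: 0.3668, which also rounds to 0.37.
- n = 32: 2.040/5.657 = 0.3605, which rounds to 0.36.

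The normal version, 1.96/√n, gives 0.358 at 30 and 0.346 at 32. It rounds to 0.37 only at n = 28. The plan's figure is therefore the t version at 30, as its own sentence says.

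**Size of the discrepancy.** 0.3734 − 0.3605 = 0.0129 SD, or 0.0129/0.3734 = about 3.5%.

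**The Aim 2 slope figure.** For a simple regression, half-width divided by slope is t(0.975, n−2) × √[(1−r²)/(r²(n−2))]. The documents give no correlation r, so r is an assumption here.

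| assumed r | n = 30 | n = 32 |
|---|---|---|
| 0.4 | 0.887 | 0.854 |
| 0.5 | 0.670 | 0.646 |
| 0.6 | 0.516 | 0.497 |

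The stated 0.67 fits n = 30 with r = 0.50, but n = 32 with r = 0.486 gives it too. This figure cannot settle which n was used.

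**What the figure is attached to.** The 0.37 SD describes a change in e-cigarette episodes per day between two weeks. Study 2 observes one week of dual use (Overview; Table 1, days 1 to 7). Its primary outcomes are withdrawal and e-cigarette satisfaction (Section 2, e. Primary Outcome). Replacing 30 with 32 would leave the figure on a quantity that Study 2 does not observe.

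**Male-female difference.** Assume one summary value per person, equal variances and a two-sample t interval. With g per sex, the half-width is t(0.975, 2g−2) × √(2/g).

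- g = 15: 2.048 × 0.3651 = 0.748 SD.
- g = 16: 2.042 × 0.3536 = 0.722 SD.

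**The case against.** The strongest reply is that this is editorial. The study is a pilot without a power claim, and targeted enrolment is 32. The precision is worded as an upper bound, and at 32 the half-width of 0.36 SD still meets a bound of 0.37. All of that stands, so the point is minor in size. It does not remove the contradiction between the sections.

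Thirty might also be the evaluable number out of 32. That is plausible, but no section says so.

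On the sex comparison, the plan does carry a second precision figure, the 0.67 labelled Aim 2, so 0.37 SD is not its only one. But the slope's predictor and size are not stated. If the predictor were sex at 15/15, 0.67 would presuppose a difference of about 0.748/0.67 = 1.1 SD, which nothing in the plan supports. It is also fair to say that a male-female half-width about twice that for one mean would arise at any total. The gap in the precision statement is therefore separate from the 30-versus-32 mismatch. Finally, the plan intends mixed models for repeated measures, so 0.72 and 0.75 SD are planning approximations.

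A reader might infer that 15 per sex is an enrolment quota, that both strata would close at 30, and that the target could never be reached. The documents do not support this. The split appears only as a parenthetical description, and no section ties it to a quota or an enrolment stop. The recruitment paragraph's "to reach sample size of n=30 32 in 1 year" might seem a further contradiction, but it may be a strike-through lost when the text was read from PDF. No weight is placed on it.

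**Conclusion.** Wrong as written, and minor in size. The total of 32 is paired with a split summing to 30 in two sections and with a split summing to 32 in another, and it is justified by a calculation for 30. No stated loss allowance reconciles them. The numerical effect on one mean is about 0.013 SD in the conservative direction, so it would be too strong to say that the plan's upper bound fails at 32.

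Two matters in the same paragraph need attention at the same time. The Aim 1 precision refers to a two-week change that Study 2 does not observe. No directly usable precision is given for the sex comparisons in Aims 2 and 3. The half-widths for one mean rest on a t interval with one value per person. Those for the sex difference also assume equal variances.

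**What to change.** 1. Use one total and one split in the Study 2 summary, the Research Plan overview, Subject Population and Justification of Sample Size. Either write 32 (16 males and 16 females), or write 32 enrolled with 30 evaluable (15 per sex) and state the assumed loss of 2 participants with its reason.
2. Recompute the precision at that number for a quantity Study 2 measures, in place of the change from week 1 to week 2. For a person-level mean withdrawal or satisfaction score, the 95% half-width is 0.36 SD at 32 or 0.37 SD at 30, in units of the between-person SD of that score.
3. Add the male-female half-width, about 0.72 SD at 16/16 or 0.75 SD at 15/15, with its assumptions: one summary value per person, equal variances and a two-sample t interval. If the slope figure is kept, name its predictor and the assumed correlation, and recompute it at the chosen number.

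The cost is wording only: no added participants, visits or analyses. The price is that a wider interval is shown openly for the sex comparisons.

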Study visit *	Baseline study visit (\$15)		a						F/U visit (\$15) and payment for EMA	\$30
Remuneration for EMA		Participant completed smart-phone based Ecological Momentary Assessments								\$50
85% EMA completion incentive										\$14
CO breath test: On-time/valid sample, regardless of the CO value (split for am/pm payment)		\$2 (\$1/\$1)	\$4 (\$2/\$2)	\$6 (\$3/\$3)	\$8 (\$4/\$4)	\$10 (\$5/\$5)	\$12 (\$6/\$6)	\$14 (\$7/\$7)		\$56
*Study visit activities: a) Review EMA procedures via phone									TOTAL:	\$150

Length of Study Visits

Baseline: 1.5 hours

STUDY 2 Follow-Up (Day 8-10): Up to 30 minutes

e. **Primary Outcome:** The primary outcomes are daily mean withdrawal scores (measured 3x/day with the Mood and Physical Symptoms Scale) and satisfaction with e-cigarette (measured daily with a 1-10 Likert scale).(65)

STUDY 2

f. **Baseline assessments Demographics:** age, gender, race, ethnicity, and level of schooling completed. **Combustible Tobacco Product Smoking:** Structured Timeline Follow-Back (TLFB) interviews will document the # of combustible tobacco products smoked per day during the past 28 days.(66) **E-Cigarette Use:** Structured TLFB interviews will document the # of episodes of e-cigarette use per day during the past 28 days. We will also query participants about nicotine concentrations used, flavors used, and the mls of liquid used/day. We already have extensive experience with the collection of these measures from work with adolescent e-cigarette users in the Yale TCORS project. **Nicotine Dependence:** Fagerstrom Test of Nicotine Dependence-R, a 6-item scale to estimate the severity of dependence.(67) **Abstinence Self-Efficacy:** The Smoking Self Efficacy Questionnaire to measure self-efficacy.(68) **Preferred Product Features:** Participants will be asked to bring their preferred cigarette and e-cigarette to the baseline visit. We will record the brand/type of cigarette and e-cigarette (brand, nicotine concentration, flavor, battery voltage, tank/cartridge size, propylene glycol/vegetable glycerin ratio).

STUDY 2

g. **Time based and Event based sampling procedure (EMA):**

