Daily Momentary Assessments: Participants will be randomly prompted with the MetricWire app up to 3x daily to provide data on e-cigarette/combustible tobacco product use in the last 15 minutes, the type of e-cigarette/combustible tobacco product used (brand/type), subjective factors (withdrawal) and the contextual factors surrounding the episode. **Subjective factors** will include *Mood* and *Withdrawal*. To maintain brevity during the random prompts, We will use the Mood and Physical Symptoms Scale (MPSS) to measure severity of five withdrawal symptoms (depressed, irritable, restless, hungry and poor concentration) and urge to smoke (craving).(65) Total score ranges from 5 to 25 with a higher score indicating a higher severity of withdrawal symptoms, we will use the International Positive and Negative Affect Schedule Short Form's measures of negative affect.(69) Participants will rate on a 5 point scale their agreement with experiencing the following emotion: (upset, hostile, ashamed, nervous, afraid). **Contextual factors** will include questions about *Companionship* (“During this smoking/vaping episode, who were you around?”) (smoker, person who is vaping, non-smoker, alone)), *Location* (“Where were you?”) (home, work/school, vehicle, bar/restaurant/store, other)), and *Activity* (“What were you doing?”) (eating/drinking a non-alcoholic beverage, drinking alcohol, working/reading/studying, traveling, socializing, other)). Participants will have 30 minutes to respond to random prompts; otherwise data will be considered lost. Each random prompt will be date- and time-stamped and record whether the assessment was completed, missed, delayed, or disbanded. *This method aims to accrue a representative sample of occasions focused on the participants' immediate state.*

STUDY 2

Daily Electronic (e-) Diaries: Participants will fill in daily night-time e- diaries via the app to provide data on e-cigarette use (episodes of e-cigarette use/ day) and combustible tobacco product smoking (# combustible tobacco products smoked/day). They will provide a rating of satisfaction with the e-cigarette they used during the day, and overall satisfaction rating of using their e-cigarette (1-10 Likert scales). Participants will record pictures of the e-cigarette(s) used during that day via the MetricWire app and provide a description of features. *We have chosen daily night-time e-diaries to minimize participant burden.*

STUDY 2

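### For withdrawal, the named primary outcome is a daily mean without a product label, but Aim 1 needs a within-person contrast between e-cigarette and combustible episodes, which only the prompt-level score carries.

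*Combined protocol and SAP*

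**What the plan says.** **Outcome.** Research Plan, item e (Primary Outcome): "The primary outcomes are daily mean withdrawal scores (measured 3x/day with the Mood and Physical Symptoms Scale". Its co-primary is a daily satisfaction rating for the e-cigarette.

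**Aim.** Aim 1, repeated in the Analysis Plan, asks how within-person ratings "change between episodes of e-cigarette use vs. episodes of other combustible tobacco product use". Hypothesis A uses the same unit: young adult dual users, particularly males, "will report lower satisfaction and higher withdrawal scores with episodes of e-cigarette use". The Study 2 summary describes "ratings of satisfaction and withdrawal) and contextual factors (location, activity, social cues) associated with each episode of use", and the Research Plan overview says the same.

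**Data.** Item g, Daily Momentary Assessments, has the app prompt participants at random "up to 3x daily to provide data on e-cigarette/combustible tobacco product use in the last 15 minutes". The same prompt asks product type and the withdrawal items. The nightly diary counts e-cigarette episodes and combustible products for the day. On satisfaction it says: "They will provide a rating of satisfaction with the e-cigarette they used during the day".

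**Analysis.** The Analysis Plan (item 11) repeats the episode contrast and specifies random subject effects. It does not say whether the repeated measure is a prompt or a day, and gives no rule for prompts that report both products or neither. It also refers to periods of e-cigarette and of combustible use, whereas Study 2 has a single dual-use week.

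**The concern.** The outcome and the aim have different units. A daily mean of up to three scores belongs to a day, and in a dual user a day has no single product. The aim needs a score attached to a product. The plan collects that score, and its outcome definition then averages it away.

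Statistical Consideration makes effect sizes with 95% intervals the product of each Aim, so the choice of unit bears on what the pilot delivers. An analyst who takes the outcome paragraph literally must reintroduce product at day level. One way is to label whole days. The other is to regress daily means on the share of prompts with each product. Neither is described in the documents. The first shrinks the contrast and the second widens its interval.

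**Working it through.** **The plan's own precision figure.** For a paired mean change, the half-width in SD units is t(0.975, n−1)/√n. With n = 30 this is 2.045/5.477 = 0.373, which matches the stated 0.37. That figure concerns change in e-cigarette episodes per day from week 1 to 2. It says nothing about withdrawal, so the plan gives no precision for the Aim 1 contrast.

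**Inputs from the documents.** 32 participants, 7 days, up to 3 random prompts a day, a 15-minute look-back. This gives at most 3 × 7 = 21 prompt scores per person (672 in all) against 7 daily means (224 in all).

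**Assumed inputs.** E episodes a day of each product, a 16-hour waking day, 85% prompt completion, independent use of the two products on all 7 days, residual SD 1, and a true contrast of 1 residual SD.

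**How many prompts carry a label.** The chance that a prompt follows use of a given product is p = 1 − exp(−E × 0.25/16). The no-use share is (1−p)². The chance that a scheduled prompt is completed and shows one given product alone is q = 0.85·p·(1−p). The chance that a person has at least one single-product prompt for each product is 1 − 2(1−q)²¹ + (1−2q)²¹.

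| E per day | p | No-use prompts | q | Chance of both | Of 32 |
|---|---|---|---|---|---|
| 1 | 0.0155 | 97% | 0.0130 | 0.055 | 1.8 |
| 5 | 0.0752 | 85% | 0.0591 | 0.515 | 16.5 |
| 10 | 0.1447 | 73% | 0.1052 | 0.813 | 26.0 |

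At these rates the daily mean is mostly an average of moments with no recent use.

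**Prompt level against daily mean.** At E = 5, data were simulated (1,000 replicates per setting) and analysed in two ways. The first was a within-person regression of the prompt score on e-cigarette only, combustible only and both, with no use as reference. The second was the same regression of daily means on the daily shares of those categories, weighted by completed prompts. Both were roughly unbiased. The standard errors of the contrast were:

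| Person-to-person SD of the contrast | Prompt | Daily mean | Ratio |
|---|---|---|---|
| 0 | 0.233 | 0.409 | 1.76 |
| 0.5 | 0.262 | 0.429 | 1.64 |
| 1.0 | 0.330 | 0.479 | 1.45 |
| 1.5 | 0.419 | 0.552 | 1.32 |

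Repeat runs with small changes in model detail gave 1.6 to 1.7 in the first row and 1.4 to 1.5 in the third.

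**Labelling whole days.** If one of three prompts follows e-cigarette use and the others follow none, the daily mean carries one third of that prompt's departure from the no-use level. The contrast therefore shrinks, by an amount that depends on the labelling rule. The plan states no rule, so no figure is given.

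**Light use.** Entry requires little; for e-cigarettes, "use e-cigarettes on at least one day during the past 7 days". With 5 episodes of each product on only one day of the week, about 1 of 32 participants contributes both products. The prompt-level standard error is then about 0.60 to 0.65, and the ratio is still about 1.6 to 1.7.

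**Interval method.** As the contrast SD rises from 0 to 1.0, the prompt-level standard error rises from 0.233 to 0.330. A model with only a random intercept does not reflect this: simulated coverage of its nominal 95% interval was 85% at contrast SD 1.0, against 95% when everyone had the same effect.

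**The case against.** The strongest reply is that the Analysis Plan already restates the episode contrast, models repeated measures within a person, and never instructs anyone to analyse daily means. A sensible analyst could simply work at prompt level. That possibility is real, and a reader should not infer that the plan commits Aim 1 to a day-level analysis. But working at prompt level would depart from the named primary outcome, and nothing in the plan authorises that.

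Second, days are not wholly unlabelled, because the diary counts each product. That is correct. Day-level counts still cannot show which product preceded a given withdrawal score.

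Third, the harm is limited. This is a pilot with no stated test or decision threshold, and one day-level route is roughly unbiased. This also stands. A reader might infer that the daily mean makes the Aim 1 estimate biased or unobtainable. The documents do not support that: the prompt data are collected, and the likely loss is precision unless days are labelled outright.

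Fourth, the prompt-level contrast could itself be nearly inestimable among light users. This stands too. Averaging adds no product information, so it is a reason to report contributor counts rather than to keep the daily mean.

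**Conclusion.** The concern holds for withdrawal, as an inconsistency between the stated outcome and the stated aim that the analysis text does not resolve. This rests on the wording alone and needs no assumption.

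The size is illustrative. At 5 episodes a day of each product over all 7 days, the daily-mean interval is about 1.4 to 1.8 times as wide when the contrast SD between people runs from 0 to 1.0, and about 1.3 times at 1.5. The use rate, waking day, completion, independence of use and size of contrast are all assumed. The 85% no-use share is likewise not a forecast.

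Two further inferences go too far. The correction does not secure a precise contrast, because labelled prompts may be scarce. Nor does it repair satisfaction, which is rated nightly for the e-cigarette only and has no combustible comparator. The item g heading mentions event-based sampling, but its text describes only random prompts and a diary. That needs separate reconciliation; if event entries were intended, the capture counts above are too low.

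**What to change.** **Primary Outcome (item e).** Name the Aim 1 withdrawal outcome as the prompt-level score. Classify each prompt by use in the last 15 minutes as e-cigarette only, combustible only, both or none. Keep the daily mean as a descriptive summary.

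**Analysis Plan (item 11).** Replace the reference to separate use periods with this classification. Estimate the within-person contrast of e-cigarette-only with combustible-only prompts in the planned mixed model, centred within person and with a sex-by-product term. Use a 95% interval that allows the contrast to vary between people. Report the number of prompts in each category and the number of participants who contribute both products.

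**Cost.** Wording in two places. No new items, visits or app changes are needed, because product use and withdrawal are already asked together. An interval that allows for varying effects is wider than a random-intercept one when effects do vary. The change creates no data, so if use is light or confined to a few days the contrast may be imprecise or only descriptive.
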